Title of Study: Toileting at Night in Older Adults: Light to Maximize Balance, Minimize Insomnia

NCT number: NCT01350505

Date of document: 9/26/18

Initial protocol

Study Procedures

Subjects will be initially phone screened before being asked to come to the lab for a screening visit. By including the phone screen, we have found that our failure rate during the screening visit is relatively low (around 20%). Our previous experience indicates that relatively few of the randomized subjects will be disempaneled. Subjects will be randomized after passing their lab screening visit; subjects who are disempaneled will be replaced. Subjects will be block randomized in three groups of nine (three in each condition), with drop-outs replaced. In-person screening will consist of discussion and signing of the consent form and completion of the following forms or tests: demographics, medication/health log, Owl and Lark Questionnaire ('morningness'/'eveningness'), Ishihara Color Plate (color blindness), Mini Mental State Exam (dementia), Pittsburgh Sleep Quality Index (sleep disorders), Geriatric Depression Scale, AUDIT (alcoholism), Balance Self-efficacy Scale (self-assessed balance), Nocturia, Nocturnal Enuresis and Sleep-interruption Questionnaire, Octopus 900 (peripheral vision), and ETDRS (visual acuity).

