After 2 hours in darkness subjects, will be awakened by the technician into one of the three experimental lighting conditions (dim white light, room light, dim orange light) and be kept awake for 13 minutes. Subjects will be tested with the same sequence as at baseline. Following the 13-minute experimental light exposure, subjects will be allowed to sleep in darkness until their typical wake time. Upon awakening, subjects will be given a subjective test of alertness (Stanford Sleepiness Scale), an objective test of alertness (Psychomotor Vigilance Test), and a questionnaire regarding the previous night of sleep (Groningen Sleep Quality Questionnaire). They will then be provided a standard hospital breakfast and discharged.

Exposure to the experimental light will always start two hours after habitual bedtime and last 13-minutes. The first two conditions, very dim white light (0.5 lux, low mesopic range) and dim white room light (5 lux). The illuminance will be confirmed with a photometer (IL1700, International Light, Peabody MA). The orange light condition will be produced by filtering the fluorescent lamps with an acrylic filter (Roscolux #19 "Fire", Roscolux, Glendale CA) so as to produce 1×10^{13} photons \cdot cm $^{-2}$ \cdot s $^{-1}$ or an equivalent LED light.

As a follow-up to this original protocol, subjects who completed all three of the visits previously described, and who indicated a willingness to be recontacted, will be asked to sign a new consent form and participate in a single overnight visit (with preceding at-home sleep monitoring) identical to the described, except that they will be awoken into normal room light (150 lux).

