Title of Study: Toileting at Night in Older Adults: Light to Maximize Balance, Minimize Insomnia

NCT number: NCT01350505

Date of document: 9/26/18

Initial analysis plan

To test our Primary Hypothesis that a long wavelength light stimulus delivered at night will improve gait and not change alertness, we will examine stride-to-stride variability in speed and change in EEG delta power as our two primary outcome measures. Statistical significance will be determined with independent repeated measure analyses of variance (ANOVA) with *post hoc t*-tests. Our *a priori* hypothesis is that gait will be progressively improved such that dim light < orange light = room light and that alertness will be improved such that dim light = orange light < room light.

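### The SAP predicts that gait under orange light equals gait under room light, but plans only tests of difference, which cannot support that equality

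*SAP*

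**What the plan says.** The SAP (Initial analysis plan) names its endpoints: "we will examine stride-to-stride variability in speed and change in EEG delta power as our two primary outcome measures". Its Primary Hypothesis is that "a long wavelength light stimulus delivered at night will improve gait and not change alertness". It then gives a more detailed prediction for gait: "gait will be progressively improved such that dim light < orange light = room light".

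The inference is one sentence: "Statistical significance will be determined with independent repeated measure analyses of variance (ANOVA) with *post hoc t*-tests". Neither document states an alpha, power, effect size, SD, equivalence or non-inferiority margin, or confidence-interval rule.

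On numbers, the Protocol (Study Procedures) says: "Subjects will be block randomized in three groups of nine (three in each condition), with drop-outs replaced". Its follow-up paragraph refers to "subjects who completed all three of the visits previously described", which implies that each subject receives all three lights.

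**The concern.** The gait prediction has two parts that need different kinds of evidence. That orange beats dim light is a superiority claim, and a t-test against zero difference suits it. That orange matches room light is a claim of no material difference. A test whose null hypothesis is zero difference can reject that claim but can never establish it.

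With no margin and no interval rule, the only planned output consistent with the equality is a non-significant orange-versus-room comparison. That result becomes more likely as the sample shrinks or the gait measurement gets noisier. If it were used as support, orange light could be reported as matching room light on a primary outcome when it delivers materially less of the benefit.

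The alertness prediction also contains an equality, but for another outcome and another pair of lights (orange and dim). A rule written for alertness would leave this comparison uncovered.

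**Working it through.** **Inputs.** From the Protocol: 3 × 9 = 27 subjects. From the SAP: ANOVA with post hoc t-tests. There is no sample-size or power figure in the plan to reproduce. Assumed: two-sided 0.05 without multiplicity adjustment; lower stride-to-stride variability is better; 27 subjects with all three lights (the three-visit reading), effects in SDs of the paired difference; or, as the alternative reading, 9 unpaired subjects per condition, effects in between-subject SDs.

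**1. Orange-versus-room t-test, 27 paired.** P(non-significant) = P(|T| ≤ 2.056), where T is noncentral t with 26 df and noncentrality δ√27 = 5.196δ.

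| True orange deficit δ | Noncentrality | P(non-significant) |
|---|---|---|
| 0.3 SD | 1.56 | 68% |
| 0.4 SD | 2.08 | 48% |
| 0.5 SD | 2.60 | 29% |

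**2. Same test, 9 per condition unpaired.** The df are 16, the critical value is 2.120 and the noncentrality is δ√(9/2). If orange gives half of a room-versus-dim benefit of 1.0 SD, δ = 0.5, the noncentrality is 1.06 and the test is non-significant 83% of the time. For benefits of 0.8, 1.5 and 2.0 SD the figures are 87%, 68% and 49%.

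**3. Whole predicted pattern, 27 paired.** Simulation with 40,000 trials per setting, three conditions, paired-difference SD of 1, and orange exactly halfway between dim and room. The pattern counts as seen if the ANOVA is significant, orange and room each beat dim, and orange versus room is non-significant.

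| Room-versus-dim benefit (SD) | P(pattern seen) |
|---|---|
| 0.2 | 3% |
| 0.3 | 7% |
| 0.4 | 12% |
| 0.5 | 19% |
| 0.6 | 26% |
| 0.8 | 32% |
| 1.0 | 25% to 26% |
| 1.2 | 14% |
| 1.5 | 4% |
| 2.0 | 0.1% |

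With small benefits the pattern is rare because orange seldom beats dim. With large ones it is rare because the orange deficit is detected.

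**4. A check that needs no SD.** Suppose the trial has 80% power for the full room-versus-dim benefit. That corresponds to 0.560 SD (27 paired) or 1.407 SD (9 per condition). At half of that benefit, the orange-versus-room test is non-significant about 71% of the time under either design. With 90% power (0.648 or 1.629 SD) it is about 63%. These figures are for that one test, not the whole pattern.

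**5. What the sample could support instead.** The 95% CI half-width for orange minus room is 2.056/√27 = 0.40 SD of the paired difference, or 2.120 × √(2/9) = 1.00 between-subject SD if unpaired. By normal approximation, showing that orange is no worse by a margin m, with one-sided 0.025, 80% power and a true difference of zero, needs n = ((1.960 + 0.842)/m)² paired subjects: 50 at m = 0.4 SD, 32 at 0.5 and 22 at 0.6. With 27 subjects the smallest such margin is 2.802/5.196 = 0.54 SD.

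**The case against.** **The SAP never says that a non-significant t-test will be read as equality.** This is correct. A reader might infer that rule, but it is not written. What the text supports is that no rule is given for the equality, and that no planned test could supply one.

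**The headline gait hypothesis is superiority.** This also stands. The Primary Hypothesis asks only that gait improve, and difference tests can address that. The equality sits in the predicted ordering. A reader might go further and say that the case for orange light depends on matching room light; neither document says so. The equality is nonetheless a pre-declared prediction on a primary outcome.

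**The error may be rare.** In part this stands. A reader might conclude that the plan would often produce the predicted pattern falsely. With orange at half benefit and 27 paired subjects, the pattern never exceeds about one third of trials, and it nearly vanishes for large benefits. The documents do not say where on that range the trial lies.

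**Sample size.** A reader might take the blocks of nine to mean that each comparison rests on nine paired subjects. Neither reading supports that: the text gives 27 subjects in total, either seen under all three lights or split nine per condition.

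**Conclusion.** The point holds as a mismatch between one part of the a priori gait prediction and the method planned for it. The ANOVA and t-tests can support the dim-versus-orange part. They cannot support the orange-versus-room equality, and this follows from the form of the test whatever the SD or design.

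The size of the risk does depend on assumptions that the documents do not settle. With 27 paired subjects, an orange deficit of 0.3 to 0.5 SD is missed 68% to 29% of the time, and the full pattern at half benefit occurs in about 0% to 32% of trials for room-versus-dim benefits of 0.2 to 2.0 SD, peaking near 0.8 SD. With 9 unpaired subjects per condition, half of a 1.0 SD benefit is missed about 83% of the time. This should be corrected, but it does not undermine the test of whether orange light improves gait relative to dim light.

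**What to change.** In the SAP, for gait:

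- State that a non-significant orange-versus-room t-test will not be taken as equal gait.
- Report the orange-minus-room difference in stride-to-stride variability with its 95% CI.
- Claim that orange is equivalent to room light only if the CI lies wholly within a margin that the investigators justify and set before analysis. For a claim of no worse than room light, the limit on the unfavourable side must lie within that margin. Retaining a stated fraction of the room-versus-dim benefit is one option, but the fraction is itself a margin, and passing it shows only that at least that fraction is kept.
- If the criterion is not met, or no margin can be justified, report the estimate and CI and make no equality claim.
- State which condition room light means in this comparison. The Protocol describes the two white conditions as "very dim white light (0.5 lux, low mesopic range) and dim white room light (5 lux" but uses an ordinary-room-lighting label for 150 lux in the follow-up visit. These passages must be reconciled.

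The cost is a few sentences and one interval on data already planned, with no extra subjects or visits. The drawback is that the claim becomes harder to win. With 27 paired subjects, a no-worse-than margin below about 0.54 SD of the paired difference would have less than 80% power even if the two lights were truly equal, so the trial may end with only the estimate and its CI.
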